## 2.3 RISK/BENEFIT ASSESSMENT

### 2.3.1 KNOWN POTENTIAL RISKS

#### Risk of the study intervention

Cannabidiol (CBD) has been used alone and in combination with tetrahydrocannabinol (THC) in numerous clinical trials and is approved with THC to treat spasms in patients with multiple sclerosis in more than 20 countries. Scientific studies using only CBD are more limited, involving <10,000 patient-years, with limited data on long-term AEs. Data from open-label and RCTs in epilepsy reveal a consistent profile of AEs (3, 27, 51). Serious adverse events (SAE) were more common in the CBD group than in the placebo groups (e.g., 16% vs. 5%), and AEs led to the withdrawal of CBD-treated patients more than those in the placebo group (e.g., 8/61 v. 1/60). The large majority of AEs were mild to moderate in severity. Adverse effects (AEs) seen more frequently in the CBD group included somnolence (36% in the CBD group vs. 10% in the placebo group), loss of appetite (28% vs. 5%), and diarrhea (31% vs. 10%) (3, 27, 52, 53). Abnormalities of hepatic aminotransferase levels occurred most often in patients taking valproate, suggesting an interaction in which CBD may potentiate a valproic acid-induced change in hepatic aminotransferase levels (3). Nevertheless, the FDA label for Epidiolex (Reference ID: 4282447) does note that the incidence of ALT elevations in patients who were not taking valproate or clobazam was 3%. The label also notes that “resolution of transaminase elevations occurred with discontinuation of Epidiolex

or reduction of Epidiolex and/or concomitant valproate in about two-thirds of cases. In about one-third of cases, transaminase elevations resolved during continued treatment with Epidiolex, without dose reduction.”

Other AEs reported more frequently in the treatment group include upper respiratory tract infection, pyrexia, and vomiting. Possible AEs of CBD that were not more common in the CBD versus placebo groups included headache, dizziness, fatigue, oral numbness, dry mouth, neck pain, feeling strange, depression, lack of taste or changed taste, feeling weak, falls, shakiness, muscle stiffness, unusual dreams, nosebleeds, hot or cold flashes, heartburn, trouble swallowing, and decreased pulse (3, 4, 27, 52, 54).

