### 4.2 SCIENTIFIC RATIONALE FOR STUDY DESIGN

Suggested dosing to address psychiatric symptoms may be substantially lower compared to dosing in epilepsy studies, which has been the focus of most pediatric CBD research. Further, previous research suggests that CBD has dose-dependent effects on social behavior and anxiety. Therefore, prior to conducting a double-blind trial, identifying optimal dosage is imperative. The BOIN design was employed as our dose finding approach. The BOIN design is flexible and sensitive to nonlinearity, and enables the designation of an optimal dose level based upon the proportion of participants who respond to the treatment.

The BOIN design allowed us to test the intermediate dose (n=9) and the low dose (n=6) and to observe a non-significantly higher rate of response (44%) on the intermediate dose than on the low dose (16%). Based on the overall excellent safety profile in part 1 (all participants completed treatment without any

severe adverse events or need to discontinue treatment) and the suggestion that higher doses of CBD may particularly target striatal D2Rhigh receptors, we have modified the second part of the trial to administer only the still untested 9 mg/kg/day dose, and to focus on participants who present with both ASD and ADHD, as they appear to be the ones most likely to be classified as responders in part 1. This is described in further detail on pages 17-20.

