#### 4.3 JUSTIFICATION FOR DOSE

Chronic CBD dosing up to 1500 mg/day has been reported to be tolerated well without AE (60-63); minor AE were reported after CBD use in children with epilepsy being treated with multiple other medications in doses up to 50 mg/kg/day (3, 27). Accordingly, we believe an upper limit of 9 mg/kg/day orally in our dose finding approach is reasonable and safe. Our proposed dosage range is substantially lower than most pediatric studies registered in ClinicalTrials.gov (accessed on 06 February 2018). Our dose range (3-9 mg/kg/day) is comparable to the only ongoing study specifically addressing behavioral symptoms in ASD (NCT02956226; dose range 1 mg/kg/day to 10 mg/kg/day). As mentioned, participants assigned to the highest dose (9 mg/kg/day) will be instructed to take half the dose (4.5 mg/kg/day, divided in two doses) per day for the first week of treatment before increasing to the full dose to minimize the chance for adverse events upon treatment initiation. This will go into effect when the next cohort of participants begin treatment with CBD; therefore, all participants who have already been enrolled will not be re-consented or informed of the changes.

The BOIN design, discussed in detail within the Dosing and Administration section of the protocol, was informed by the observation of dose-dependent inverted-U effects on social behavior in a mouse model of Dravet syndrome in which social effects were observed at lower doses than anti-seizure effects (2), the increased efficacy of CBD in reducing anxiety during a public speaking task at a moderate dose compared to a low and high dose (9), and correspondence with [name] regarding his clinical experiences in prescribing CBD to address associated symptoms of ASD. As noted, now that we've obtained data from 15 participants on the low and intermediate doses by implementing the BOIN design, we propose to test the remaining 9 mg/kg/day dose in up to 15 participants – within the originally approved accrual ceiling of 30.

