    - Non-response: no-to-minimal therapeutic benefit captured by a CGI-I score of 3 (minimally improved) or greater (i.e., no change or any worsening) determined by consensus as indicated above, and/or severe AE, defined as severe cognitive or behavioral toxicity, impaired liver and renal function, or impaired hematopoiesis that is deemed to be potentially or likely related to study medication (also see section 8.3.2), causing early discontinuation of study intervention.

While applying a uniform statistically derived algorithm for defining treatment response and non-response for all patients would have been preferable, the above procedures were implemented given the exploratory nature of the study and the wide range of therapeutic effects that CBD may exert. The intent of this exploratory study has been to provide the foundation for a well-defined subsequent RCT.

Over the first 15 participants, we have identified five as responders, for an overall response rate of 33%, and a response rate of  $4/9 = 44\%$  on 6 mg/kg/day, as opposed to the 60% rate anticipated on the optimal dose. The response rate on 3 mg/kg/day was  $1/6 = 16\%$ . Per the BOIN design that we implemented, we have excluded both the 6 mg/kg/day and 3 mg/kg/day dose for further testing. We believe that it would be scientifically valuable to test the 9 mg/kg/day dose on the remaining 15 participants that were originally approved for this open trial. The purpose would be to further confirm the overall safety of the AE profile – which is likely given the pediatric experience with 10 mg/kg/day and 20 mg/kg/day in patients with refractory epilepsy who are more medically fragile. It has also been hypothesized that higher doses of CBD may have preferential effects on D2high receptors in the striatum. If so, that might explain why all five responders had ASD, as well as ADHD.

Accordingly, we now request that we amend the open trial to test only the dose of 9 mg/kg/day and that we require the combination of ASD and ADHD for inclusion. All other aspects of the trial would be unchanged, other than adding the Strengths and Weaknesses of Attention-Deficit/Hyperactivity Disorder Symptoms and Normal Behavior (SWAN) as a dimensional measure of ADHD and completing the K-SADS-COMP at the screening visit rather than the baseline/enrollment visit so that the study clinicians can confirm the presence of an ADHD diagnosis.

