Given our experience with the first 15 participants, we anticipate that at least 1/3 will be classified as responders. If none of the first 6 participants on 9 mg/kg/day are responders, then we would eliminate the dose and terminate the trial. A low, non-zero response rate, as shown below in Table 3, would also determine terminating the trial, as it would be tantamount to evidence that the optimal dose was 6 mg/kg/day, our initial starting dose.

**Table 3.** Dose elimination rules for cohorts 6 to 10

Cohort	1	2	3	4	5	6	7	8	9	10
Number of participants to be treated at the current dose	3	6	9	12	15	18	21	24	27	30
Dose administered (mg/kg/d)	6	6	3	3	6	9	9	9	9	9
Cumulative N of respondents	1	3	4	4	5	-	-	-	-	-
Terminate if # of responses <=						NA	5	6	7	

Thus, we propose to enroll at least six more participants on the dose of 9 mg/kg/day. If none of them respond, the cumulative number of respondents would remain 5, and we will discontinue the trial; if at least 1 responds within the first 6, we will enroll 3 additional participants. If the total number of responders remains 6, we will discontinue the trial. If the number of responders is 7 or more after 9 participants are enrolled, we will enroll an additional 3 participants for a total of 12 on this dose. If the number of responders does not increase beyond a total of 7, we will terminate due to likely futility.

Table 4 provides the operating characteristics of this design extension for a variety of true response rates.

**Table 4.** Operating characteristics of 9 mg/kg/day evaluation

	Dose 1	Dose 2	Dose 3	Dose 4	Dose 5
True response rate	0.1	0.2	0.3	0.4	0.5
Probability of early termination(%)	90.4	60.8	31.0	11.9	3.5

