#### 9.4.4 SAFETY ANALYSES

Safety endpoints will be analyzed as summary statistics during treatment and as change scores from baselines. Adverse events will be coded per the Medical Dictionary for Regulatory Activities (MedDRA). Each AE will be counted once only for a given participant. Adverse events will be presented in terms of severity, frequency, and relationship of AEs to study intervention by System Organ Class (SOC) and preferred term groupings. For each AE, start date, stop date, severity, relationship, expectedness, outcome, and duration will be reported. Adverse events leading to premature discontinuation from the study intervention and serious treatment-emergent AEs will be presented either in a table. The information included here should be consistent with the information contained within **Section 8.2, Safety and Other Assessments**.

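### Part 2 is meant to further confirm safety at 9 mg/kg/day, but 6 to 15 children, no numeric safety boundary and adverse event tables without intervals can only describe it

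*Combined protocol and SAP*

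**What the plan says.** Section 6.1.2 gives the reason for Part 2: "The purpose would be to further confirm the overall safety of the AE profile". It adds that this outcome is expected, "which is likely given the pediatric experience with 10 mg/kg/day and 20 mg/kg/day in patients with refractory epilepsy". The same paragraph offers a receptor hypothesis as a second reason for the dose.

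On numbers, section 4.3 sets the ceiling ("we propose to test the remaining 9 mg/kg/day dose in up to 15 participants") and section 6.1.2 the floor ("Thus, we propose to enroll at least six more participants on the dose of 9 mg/kg/day"). The first boundary reads: "If none of the first 6 participants on 9 mg/kg/day are responders, then we would eliminate the dose and terminate the trial". Two later boundaries, after 9 and 12 children on this dose, also count responders. Section 9.2 says that no statistical method set the sample size.

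On analysis, section 9.4.4 plans summary statistics and tabulation: "Adverse events will be presented in terms of severity, frequency, and relationship of AEs to study intervention". It names no interval or bound. Section 9.4.3 does plan 95% confidence intervals, for the secondary measures.

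Section 4.2 justifies the move to 9 mg/kg/day in these terms: "Based on the overall excellent safety profile in part 1". The basis it gives is that all 15 children completed treatment with no severe adverse event and no need to discontinue.

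**The concern.** The word used for the purpose promises more than the design can give. Confirming an AE profile at a new dose means showing that rates above some level are unlikely. The plan names no such level, the number of children on the dose may be as low as 6, and the planned tables would show a count of zero with no statement of what zero excludes.

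Section 6.1.2 describes the study as the foundation for a later randomized trial. A statement about safety at 9 mg/kg/day that goes forward without its bound would look firmer than the data allow. Section 4.2 already uses the absence of severe events in 15 children, split 6 and 9 between two lower doses, as support for the next step without giving its precision.

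**Working it through.** **Inputs.** Looks after 6, 9 and 12 children on 9 mg/kg/day, maximum 15 (section 6.1.2, Table 3). The cumulative limits of 5, 6 and 7 include the 5 responders from Part 1, so on this dose the trial stops at 0 of 6, at most 1 of 9, or at most 2 of 12. The 3% rate is the incidence of ALT elevation without valproate or clobazam in section 2.3.1. The documents give no confidence level for safety, so 95% is assumed and shown one-sided and two-sided.

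**Step 1: check the reading of the rule against Table 4.** With true response rate p and q = 1 − p:

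- stop at 6: q^6
- stop at 9: 6·p·q^8
- stop at 12: 33·p²·q^10, where 33 = 15 + 6×3 counts the ways to have exactly 2 responders in 9 after at least 1 in the first 6.

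At p = 0.2 this gives 0.262 + 0.201 + 0.142 = 0.605.

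| True response rate | 0.1 | 0.2 | 0.3 | 0.4 | 0.5 |
|---|---|---|---|---|---|
| Table 4, % early termination | 90.4 | 60.8 | 31.0 | 11.9 | 3.5 |
| Recomputed, % | 90.5 | 60.5 | 30.5 | 11.9 | 3.5 |

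Agreement is within 0.5 points, so the reading of the rule is right.

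**Step 2: number treated at 9 mg/kg/day.** At p = 0.2, expected N = 6×0.262 + 9×0.201 + 12×0.142 + 15×0.395 = 11.0, and the chance of ending at 6 is 26%. At the anticipated one third, expected N = 6×0.088 + 9×0.078 + 12×0.064 + 15×0.771 = 13.6, and the chance of ending at 6 is 9%.

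**Step 3: what zero events excludes.** The exact upper limit for 0 of n is 1 − 0.05^(1/n) one-sided and 1 − 0.025^(1/n) two-sided. The chance of seeing an event of true rate r at least once is 1 − (1 − r)^n.

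| n | Upper limit, one-sided 95% | Upper limit, two-sided 95% | Chance of seeing a 3% event |
|---|---|---|---|
| 6 | 39.3% | 45.9% | 16.7% |
| 9 | 28.3% | 33.6% | 24.0% |
| 12 | 22.1% | 26.5% | 30.6% |
| 15 | 18.1% | 21.8% | 36.7% |

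**Step 4: the Part 1 statement.** The same limits apply to zero severe events in Part 1: 18.1% or 21.8% for all 15 children, 39.3% or 45.9% for the 6 on 3 mg/kg/day, and 28.3% or 33.6% for the 9 on 6 mg/kg/day.

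**Step 5: common events.** Section 2.3.1 also gives higher rates from epilepsy trials. By the same formula, the chance of at least one case is:

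| Event (rate) | n = 6 | n = 15 |
|---|---|---|
| Somnolence (36%) | 93% | 99.9% |
| Diarrhea (31%) | 89% | 99.6% |
| Loss of appetite (28%) | 86% | 99.3% |
| Serious AE (16%) | 65% | 93% |
| Withdrawal for AE (8/61 = 13%) | 57% | 88% |

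Fifteen children would therefore very probably show the common effects if they occurred at those rates. Even so, zero serious AEs in 15 would not exclude 16%, because both limits lie above it.

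**The case against.** A reader might infer that safety plays no part in how many children are treated. The documents do not support that. Under section 6.1.2 a responder must be free of dose limiting effects, and a severe drug-related AE leading to discontinuation is a non-response; section 7.1 extends this to any discontinuation for AEs. Investigators review safety after each cohort of three (section 4.3), the monitoring committee does so every third participant (section 10.1.6), and the study may be stopped for unacceptable risk (section 10.1.2). What stands is narrower: none of these carries a numeric threshold. Three responders among the first 12, with at least one by 6 and two by 9, take enrolment to 15 however many of the others stopped for AEs, unless judgement intervenes.

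It can also be said that one clause is being read as an objective. Section 3 lists no safety objective, section 4.1 calls all endpoints exploratory, and the sentence speaks of adding to outside experience. That is fair, and nowhere do the documents conclude that safety at 9 mg/kg/day is proven. But the sentence does assign the confirming to Part 2, and exploratory status is a reason to use a weaker verb.

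A reader might further infer that the 3% ALT risk would be overlooked. It is already disclosed in section 2.3.1, and section 8.2 schedules liver tests, so failing to observe it would hide nothing known. It serves here only as an example of a less common event.

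Finally, section 9.3 covers safety across the whole sample. With 30 children, zero events gives 9.5% one-sided or 11.6% two-sided, and a 3% event is seen with probability 1 − 0.97^30 = 60%. Pooling, however, mixes three doses and does not answer the question about 9 mg/kg/day. Individual listings and known denominators would let a reader compute the limits, but the plan should report them.

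**Conclusion.** The point holds as a mismatch between stated purpose and attainable precision. At 9 mg/kg/day, an absence of events leaves rates up to 39–46% open if the trial ends at 6 children and 18–22% if it reaches 15. Part 2 can describe common AEs; it cannot confirm that less common or serious ones are absent. The Part 1 statement in section 4.2 has the same limitation.

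The figures rest on an assumed 95% level and on treating N as fixed. The second is an approximation, since discontinuation for AEs counts as non-response and so can influence N. The benchmark rates in section 2.3.1 come largely from epilepsy patients, and no dose is given there for the 3% figure, so they show scale and do not predict rates in this trial.

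This does not make the trial invalid or unmonitored, and descriptive safety reporting suits a small open study. The change needed is to claim no more than that.

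**What to change.** 1. Section 6.1.2: state the purpose of Part 2 as describing the AE profile at 9 mg/kg/day, in line with the exploratory status in section 4.1.
2. Section 9.4.4: report any AE, severe AE, serious AE, ALT/AST elevation and discontinuation for AE as proportions with exact 95% confidence intervals, at 9 mg/kg/day and by dose for Part 1. Where no event is seen, give the upper limit at the N actually reached. State whether limits are one-sided or two-sided.
3. Section 4.2: add the corresponding upper limit to the Part 1 safety statement.

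The cost is a few sentences and one added column in the AE table. The price is a less favourable safety statement. No change to dose, enrolment or stopping rules is proposed.

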## 6.2 PREPARATION/HANDLING/STORAGE/ACCOUNTABILITY

### 6.2.1 ACQUISITION AND ACCOUNTABILITY

The drug will be shipped to the responsible person, such as the PI, who will check the amount received and the condition of the drug. Details of the drug received will be recorded in an accountability record. We will acknowledge drug receipt to Greenwich Biosciences, Inc. and will complete any receipt forms required. As directed in the investigational brochure, all supplies, including unused, partially used, or empty containers, will be returned to Greenwich Biosciences, Inc. or destroyed at the center if agreed in writing by the study monitor.

---

### 6.2.2 FORMULATION, APPEARANCE, PACKAGING, AND LABELING

The CBD will be packaged as Epidiolex (V), 100mg/mL oral solution in a 100 mL bottle. Each bottle of 100mg/mL solution will contain 100 mL of oral CBD solution. The CBD will be shipped in separate subject-specific boxes from Greenwich Biosciences, Inc. The subject drug kits will contain a 100mL amber glass bottle of 100 mg/mL CBD in sesame oil vehicle with sucralose sweetener and strawberry flavoring. The bottle will have a child-resistant cap. The bottles will be in a white cardboard carton with cardboard insert. The outer sides of carton will bear a label with appropriate instructions. The box will also contain a graduated oral syringe for accurate dosing administration and a patient information leaflet. Label text will comply with European Union (EU) guidance on Good Manufacturing Practice, Annex 13 Labelling.

---

### 6.2.3 PRODUCT STORAGE AND STABILITY

The CBD will be stored in a locked file-cabinet inside a locked office at room temperature. The CBD must be stored in temperatures less than 30°C, with limited access to light.

---

### 6.2.4 PREPARATION

Not applicable.

## 6.3 MEASURES TO MINIMIZE BIAS: RANDOMIZATION AND BLINDING

Not applicable.

## 6.4 STUDY INTERVENTION COMPLIANCE

Adherence to protocol will be assessed by requiring a participant drug log in which dose and time of administration will be recorded by the parent/guardian.

## 6.5 CONCOMITANT THERAPY

For this protocol, concomitant pharmacologic, educational, behavioral, and/or dietary therapies will be reviewed at each contact. Concomitant therapies will be reported in the Case Report Form (CRF). The subjects will be asked to continue any non-exclusionary psychopharmacologic (i.e., stimulant such as methylphenidate), educational, behavioral, and/or dietary interventions that were stable for 4 weeks prior to initiation of trial and to maintain them stable through the trial. Change in outside therapy, including pharmacological treatment, could skew results. Any participant who experiences a change of services (other than those associated with school holidays) will be withdrawn from the study as per the PI.

---

### 6.5.1 RESCUE MEDICINE

Not applicable.

## 7 STUDY INTERVENTION DISCONTINUATION AND PARTICIPANT DISCONTINUATION/WITHDRAWAL

### 7.1 DISCONTINUATION OF STUDY INTERVENTION

A participant may be discontinued from the study intervention at any time if the participant or participant's legal guardian or the investigator feels that it is not in the participant's best interest to

continue. Study intervention may be discontinued following parental withdrawal of consent, failure to remain compliant with study procedures, protocol violation requiring discontinuation, or SAE. If a participant must discontinue the study treatment, the method of CBD discontinuation will be determined based on type of reaction and/or reason for withdrawal. For example, if the participant experiences a rapidly progressive rash it would lead to abrupt cessation of CBD, but if participant experiences excess tiredness, CBD would be tapered off. A discussion of the method of cessation will occur between the participant and/or participant's parent/legal guardian and the physician.

If a participant requires discontinuation of CBD due to AEs, the participant will be considered a "non-responder." Participants who are discontinued from study intervention will receive the 3-month follow-up telephone call to gather descriptive information about current functioning and treatment choice.

While there will be no temporary discontinuations on the basis of AE, participants may experience a temporary discontinuation if a follow-up session is not attended within the +/- 3 day timeframe. In this case, the investigator will determine how to proceed based on report of effects and AEs, and results from safety assessments. If all variables indicate good tolerability, continuation will occur. The participant's participation in the trial will be extended by one week to ensure that data has been collected across three time points after enrollment/baseline. If AE is a concern, the investigator will determine if any change in participant management is needed.

The data to be collected at the time of study intervention discontinuation will include the following:

- Physical exam and vital signs
- Clinical labs (i.e., test of hepatic and hematological function including total bilirubin; plasma for CBD levels)
- AE review and evaluation
- MRI
- Standardized measures of symptom improvement (i.e., ABC, ADAMS, ASC-ASD-Child, ASC-ASD-Parent, AFEQ, BIS, CGI-I, CGI-S, HSQ-ASD, OSU Autism CGI-I, OSU Autism CGI-S, RBS-R, SCARED, SDSC, SRS-2, SWAN [Part 2], Vineland-3)

